#### **INFINITI Data Analysis Plan**

3.8. The same models described in the analysis of primary objective 1.1 will be performed for each of the different outcomes. *Note 3.8.a.i, blood urea was not collected at V4. Only perform V3-V9 change.* 

### 4. Exploratory Subgroup Analysis.

Analyses following the forms described in 1.1 will be conducted by adding a main effect of diabetes-status and a third-level interaction term for diabetes-status by time by treatment. For 2.1, the numbers of adverse events will be calculated according to diabetes status. Analyses following the forms described in 3.2 - 3.7 will be conducted by adding a main effect of diabetes-status and an interaction term for diabetes-status by treatment.

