3.3 Anticipated Outcomes

- 1. We hypothesize that dapagliflozin will result in a significant reduction in systolic and diastolic blood pressure in a cohort of KTR with or without T2D and PTDM.
- 2. We hypothesize that dapagliflozin will be well tolerated in KTR with or without T2D and PTDM, with adverse events similar to that of non-transplant populations. We also hypothesize that there will be no clinically significant changes in CNI levels or episodes of acute rejection in KTR treated with dapagliflozin vs. placebo during the study.
- 3. We hypothesize that dapagliflozin will result in a significant natriuresis, as well as reductions in arterial stiffness, albuminuria, allograft hypoxia and markers of oxidative stress, while having neutral effects on cardiac and renal function over the course of the 12-week study period.
- 4. We hypothesize that the glucose-lowering effects of dapagliflozin will be modest in KTR with T2D or PTDM due the high prevalence of CKD in this population. In participants without T2D or PTDM, we do not expect any glucose lowering.

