5.3 Sample Size

The sample size is based on the primary endpoint of blood pressure. Currently, there is only one publication from our group with information available on the effect of SGLT2i on blood pressure reduction in KTR with diabetes. In this observational study of 10 KTR and simultaneous pancreas-kidney transplant recipients treated with canagliflozin, we reported a SBP decrease of $6.5 \pm 10 \text{ mmHg}^{63}$. Given the small sample size in our observational study, we believe the standard deviation would be smaller in a larger cohort. Blood pressure reduction with SGLT2 inhibition appear to be similar between patients with and without diabetes in non-transplant studies. We, therefore, estimated the sample size based on a SBP change of 6.5 mmHg with a standard deviation of 8 mmHg. Under the hypothesis that SGLT2i decreases SBP by $6.5 \pm 8 \text{ mmHg}$ compared to placebo with a two-sided alpha of 0.05 and 80% power, we calculate a sample size of n=48, with 24 randomized to dapagliflozin and 24 randomized to placebo. Assuming a 10% attrition rate, the final sample size required is 52 participants. This sample size is similar to those successfully used in previous studies⁷¹, and sufficient to measure secondary renal endpoints related to renal hemodynamic function⁷¹, natriuresis and arterial stiffness⁷²⁻⁷⁴. Based on previous studies, we anticipate an even sex distribution in each group.

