- 2. Our study endocrinologist, [name] will be responsible for glycemic management in participants with diabetes during the study through study and telephone visits⁷¹. All antidiabetes medications will be allowed including insulin, sulfonylureas, DPP4 inhibitors, and GLP-1 receptor agonists. SGLT2 inhibitors may not be used within 1 month of starting the study. No minimum time on anti-diabetes medications will be required prior to randomization. Adjustment of insulin and other glucose-lowering medications will be

made as necessary by [name] utilizing an individualized approach based on the patients' specific risk of hypoglycemia and/or DKA. Changes in glycemic management will always made in conjunction with the patients' own endocrinologist/family doctor. Major hypoglycemic events will be captured as an adverse event of interest.

3. Given the lack of definitive data supporting the use of ACEi/ARB as a renoprotective strategy, the use of an ACEi/ARB is variable in KTR. However, these drugs are prescribed to KTR based on physician preference, and due to non-renal indications such as post-transplant erythrocytosis, hypertension or cardioprotection. The use of ACEi/ARB with SGLT2i will be permitted during the entre duration of the trial and we have incorporated frequent safety monitoring in our study to allow for the early detection of any potential adverse events that may occur with concomitant renin-angiotensin-aldosterone system blockade and SGLT2i.

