## 4. Exploratory subgroup analyses

- 4.1. Compare diabetes vs non-diabetes status groups separately, and include test of interaction
  - a. Primary objectives
  - b. Secondary objectives
  - c. Exploratory objectives

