# 1. Analysis for the primary objective:

- 1.1. To assess dapagliflozin-related acute and chronic changes in the primary outcome of seated systolic blood pressure compared to placebo, linear mixed-effects models will be used. Two separate models will be fit. For acute change, the vector of outcomes will include the baseline and 1-week values (i.e. Visit 3 and Visit 4 values). For chronic changes, the vector of outcomes will include the baseline and 12-week values (i.e. Visit 3 and Visit 9 values). The covariates will include the visit and treatment-by-visit interaction; due to randomization, a covariate for the main effect of treatment will not be included. The treatment-by-time coefficient, its 95% confidence interval, and its p-value will be used to assess the effect of treatment.
- 1.2. We will repeat this analysis with:
  - a. Seated diastolic blood pressure as an outcome
  - b. Seated mean arterial pressure as an outcome

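### The diabetes subgroup model leaves out diabetes-by-visit, so a difference in time trend between the diabetes groups would mostly be reported as a treatment interaction

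*SAP*

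**What the plan says.** SAP section 1.1 under Analysis for the primary objective sets the base model: "The covariates will include the visit and treatment-by-visit interaction; due to randomization, a covariate for the main effect of treatment will not be included". Each fit uses two time points; for the chronic effect, "the vector of outcomes will include the baseline and 12-week values". The closing notes of the SAP specify a participant random intercept and REML.

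SAP section 4 (Exploratory Subgroup Analysis) extends that model by "adding a main effect of diabetes-status and a third-level interaction term for diabetes-status by time by treatment". It names nothing else. The fitted mean is therefore visit + treatment-by-visit + diabetes + diabetes-by-visit-by-treatment.

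The Outcomes part of the SAP, item 4.1, gives the purpose: "Compare diabetes vs non-diabetes status groups separately, and include test of interaction". It applies this to the primary, secondary and exploratory objectives. The secondary objectives include glucose lowering, measured by HbA1c and fasting glucose.

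**The concern.** Without diabetes-by-visit, the placebo arm has a single visit coefficient. If participants with diabetes change differently over time from those without, whatever treatment they receive, the model can express this at follow-up only through the three-way term. That term is the interaction test. The SAP justifies dropping the treatment main effect by randomisation, but diabetes status is not randomised, so that argument does not extend to diabetes-by-visit.

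The glycaemic outcomes are where this matters most. Protocol 6.2 states "No minimum time on anti-diabetes medications will be required prior to randomization" and allows those drugs to be adjusted during the study, so HbA1c could drift in both arms among participants with diabetes only. Protocol 3.3 expects modest glucose lowering with diabetes, but "In participants without T2D or PTDM, we do not expect any glucose lowering". A drift common to both arms could be read as support for that pattern, or could hide it.

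**Working it through.** **Inputs.** SD of change 8 mmHg, effect 6.5 mmHg and 24 per arm (Protocol 5.3); 1:1 allocation (Protocol 6.1); stratified randomisation (Protocol 9.2), which supports an equal diabetic share q in the two arms; random intercept (SAP closing notes). Assumed, because the documents do not give them: delta, rho and q.

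**The plan's own figure.** 2 × (1.960 + 0.842)² × 8² / 6.5² = 23.8, so 24 per arm and 48 in total. This reproduces. The documents give no figure for the subgroup interaction.

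**Bias.** With equal q in both arms, the problem reduces to the diabetic-minus-non-diabetic contrast in four cells. Let b be the diabetes main effect and g the three-way coefficient, and set the true baseline contrast to 0.

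| Cell | Truth | Model as written |
|---|---|---|
| Placebo, baseline | 0 | b |
| Placebo, follow-up | delta | b |
| Dapagliflozin, baseline | 0 | b |
| Dapagliflozin, follow-up | delta | b + g |

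Let v be the variance of one such contrast.

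- The placebo two-visit mean has expectation delta/2 and variance v(1+rho)/2. The dapagliflozin baseline has expectation 0 and variance v.
- Inverse-variance weighting gives E(b) = (delta/2) × [2/(1+rho)] / [2/(1+rho) + 1] = delta/(3+rho).
- The estimate of g is (dapagliflozin follow-up − b) − rho × (dapagliflozin baseline − b). Hence E(g) = delta − (1−rho) × delta/(3+rho) = **delta × 2(1+rho)/(3+rho)**.

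| rho | 0 | 0.3 | 0.5 | 0.6 | 0.7 | 0.8 |
|---|---|---|---|---|---|---|
| E(g)/delta | 0.67 | 0.79 | 0.86 | 0.89 | 0.92 | 0.95 |

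A random intercept implies rho ≥ 0, so most of delta always moves into the interaction. The factor does not depend on q. With diabetes-by-visit in the model it is 0.

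**Subgroup effects.** The effect averaged over the diabetes groups is unbiased, so the effect without diabetes shifts by −q × factor × delta. For rho 0.3 to 0.8 this is −0.26 to −0.32 × delta at q = 1/3, −0.39 to −0.47 at q = 1/2, and −0.53 to −0.63 at q = 2/3.

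**Precision.** Var(g) is v(1−rho²) × 4/(3+rho) as written and 2v(1−rho²) with the extra term. The ratio is (3+rho)/2 = 1.65, 1.80 and 1.90 at rho 0.3, 0.6 and 0.8. For systolic pressure with q = 1/2, the visit variance is 64/[2(1−rho)] and v is that divided by 24 × 0.25 = 6. The corrected variance is then 64(1+rho)/6. At rho 0.6 it is 17.07 (SE 4.13 mmHg), against 17.07/1.80 = 9.48 (SE 3.08) as written. The two models have equal mean squared error at |delta| = √(17.07 − 9.48)/0.889 = 3.10 mmHg; at rho 0.3 and 0.8 this is 2.97 and 3.18.

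**False-positive rate for systolic pressure.** REML simulation with 4,000 replicates per setting, 24 per arm, half diabetic, true effect −6.5, no true interaction, and a t reference with 44 df:

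| rho | delta 0 | 2 mmHg | 3 mmHg | 5 mmHg |
|---|---|---|---|---|
| 0.3 | 5.5% | 9.2% | 11.9% | 25.3% |
| 0.6 | 5.3% | 8.1% | 13.3% | 27.1% |
| 0.8 | 5.5% | 8.9% | 14.1% | 28.4% |

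With diabetes-by-visit added, rejection is 4.7–5.8% throughout. At rho 0.6 and delta 5, the mean three-way estimate is 4.42 as written (truth 0) and the effect without diabetes is −8.71 (truth −6.5). The corrected model gives 0.05 and −6.52. With an assumed visit SD of 12 mmHg and rho 0.6, rejection at delta 5 is 18.0% as written.

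**HbA1c, illustrative, half diabetic, rho 0.3 to 0.8.**

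| Assumed delta (points) | Spurious interaction | Shift in effect without diabetes |
|---|---|---|
| −0.1 | −0.08 to −0.09 | +0.04 to +0.05 |
| −0.3 | −0.24 to −0.28 | +0.12 to +0.14 |
| −0.5 | −0.39 to −0.47 | +0.20 to +0.24 |

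**The case against.** - **The SAP does not list the term, which is not the same as excluding it.** Naming only the highest-order interaction is common shorthand, and software with factor coding would expand the stated terms to a full-rank model of 8 parameters that contains diabetes-by-visit. But that expansion also puts back a baseline treatment column, which section 1.1 excludes. The literal five-parameter model is the one consistent with the SAP's own text. At the least, the fitted model should not depend on a coding default.
- **Delta is assumed.** This stands. Protocol 6.1 has participants with diabetes continue existing therapy, and some adjustments would follow hypoglycaemia, which might differ by arm. But Protocol 6.2 allows adjustment and requires no prior stability, so a zero delta for glycaemic outcomes cannot be taken for granted.
- **Separate comparisons would answer the protocol's expectation within each group.** Separate fits would indeed give unbiased subgroup effects. The interaction test specified in section 4 would still be biased and would not equal their difference.
- **For systolic pressure this is a bias–variance trade.** This stands in part. Below about 3 mmHg the model as written has the smaller mean squared error. That advantage rests on an unstated assumption that delta is 0, and it does not restore the 5% level of the test.
- **The analysis is exploratory.** This is correct, and it limits the consequence.

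**Conclusion.** The concern holds. As specified, the interaction test by diabetes status is valid only if the change over time, treatment apart, is the same with and without diabetes. If it differs by delta, between 0.79 and 0.95 of delta (rho 0.3 to 0.8) appears as a treatment interaction, and the subgroup effects shift in opposite directions. The formula assumes 1:1 allocation, equal diabetic shares in the arms, and a delta common to both arms. The sizes in mmHg and HbA1c points depend on assumed values of delta.

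Only exploratory subgroup analyses built on the section 1.1 model are affected. The primary treatment effect is not, nor are the regressions in 3.2–3.7 if run on change values, where the diabetes main effect already does this job.

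**What to change.** In SAP section 4, write the subgroup model for all outcomes of the 1.1 form as visit + treatment-by-visit + diabetes + diabetes-by-visit + diabetes-by-treatment-by-visit. Test the last term. Report the treatment effect with its 95% confidence interval in each diabetes group from this same model, so that the comparison within groups asked for in Outcomes 4.1 and the interaction test agree. Leaving out the baseline treatment terms remains consistent with the randomisation argument in 1.1.

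The cost is a sentence of SAP text, one more parameter per model, and a real loss of precision: the interaction variance rises by 65–90% (SE 28–38% larger). For systolic pressure the corrected test needs a true interaction of about 10–12 mmHg for 80% power (2.80 × SE of 3.72 to 4.38). It should be presented as an estimate with a wide interval, not as a decisive test.

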### 3. Exploratory objectives:

- 3.1. We will determine acute and chronic effects of dapagliflozin vs. placebo from baseline on estimated plasma volume (ePV).
- 3.2. We will assess whether the proximal renal tubular natriuretic effect of dapagliflozin leads to volume contraction compared to placebo. To this end, we will determine the association between acute and chronic changes to fractional sodium handling and acute and chronic changes in volume markers.
- 3.3. We will assess whether the proximal renal tubular natriuretic effect of dapagliflozin is associated with changes in kidney function compared to placebo. To this end, we will determine the association between acute and chronic changes to fractional sodium handling and acute and chronic changes in GFR.
- 3.4. We will assess whether volume contraction with dapagliflozin leads is associated with SNS activation compared to placebo. To this end, we will determine the association between acute and chronic changes to volume markers and acute and chronic changes in markers of SNS activation.
- 3.5. We will determine whether changes in neurohormones and volume markers are associated with changes in kidney function. To this end, we will determine the

association between acute and chronic changes in absolute measures of kidney function and the acute and chronic changes in neurohormones and volume markers with dapagliflozin compared to placebo.

- 3.6. We will determine whether changes in neuro-hemodynamic & volume markers are associated with changes in arterial stiffness. To this end, we will determine the association between acute and chronic changes in arterial stiffness and the corresponding acute and chronic changes in neurohormones and volume markers with dapagliflozin compared to placebo.
- 3.7. We will determine whether changes in neurohormones and volume markers are associated with changes in blood pressure. To this end, we will determine the association between acute and chronic changes in blood pressure and the acute chronic changes in neurohormones and volume markers with dapagliflozin compared to placebo.
- 3.8. We will determine acute and chronic effects of dapagliflozin vs. placebo from baseline on urine and plasma chemistry marker levels.

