# 3. Analysis for exploratory objective:

- 3.1. ePV should be tested for equality of variances using the Welch–Satterthwaite equation.
- 3.2. 3.7. Linear regression will be performed, with treatment as a covariate. Two separate models will be fit for acute and chronic changes. Acute changes will use the baseline and 1-week values for both the dependent and independent variable values; chronic changes will use baseline and 12-week values. Exceptions include NICOM parameters will only evaluate chronic changes.

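### In the diabetes subgroup version of association models 3.2–3.7, the added diabetes-by-treatment term does not test whether the association differs; diabetes-by-marker change does

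*SAP*

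**What the plan says.** Under Exploratory objectives, the SAP gives each of 3.2–3.7 an operational sentence whose target is a relation between two changes. For 3.2 it is: "we will determine the association between acute and chronic changes to fractional sodium handling and acute and chronic changes in volume markers".

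The model is in Analysis 3.2–3.7: "Linear regression will be performed, with treatment as a covariate". Both sides of the regression are changes: "Acute changes will use the baseline and 1-week values for both the dependent and independent variable values", with 12-week values for the chronic version.

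Outcomes section 4.1 sets the subgroup aim: "Compare diabetes vs non-diabetes status groups separately, and include test of interaction". Its list covers primary, secondary and exploratory objectives.

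Analysis section 4 then gives two recipes. Models of form 1.1 receive a diabetes main effect and a three-way diabetes, time and treatment interaction. Models 3.2–3.7 receive a diabetes main effect and "an interaction term for diabetes-status by treatment". No product of diabetes status and marker change is named for them.

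**The concern.** In 3.2–3.7 the quantity of interest is the slope of the outcome change on the marker change, and treatment is there as an adjuster. A test of whether that slope differs by diabetes status must interact diabetes with the marker change. The SAP interacts diabetes with the adjuster.

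The contrast with the other recipe in the same section is telling. In form 1.1 the tested parameter is treatment-by-visit, and the three-way term lets diabetes modify exactly that parameter. The same logic applied to 3.2–3.7 gives diabetes-by-marker. The wording for 3.2–3.7 may have been carried over from the treatment-effect models.

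What is at stake is a mechanistic statement. Protocol section 4 justifies enrolling recipients with and without diabetes partly on the ground that the mechanisms are independent of glycaemic control and intact in both groups. A non-significant diabetes-by-treatment p-value could be taken as support for that claim although it says little about it. A significant one could be taken as evidence against it when only the drug effect differs.

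**Working it through.** **Inputs.** The documents give no figure for these models, so the sample size comes from Protocol section 5.3. That figure reproduces: n per arm = 2 × (1.960 + 0.842)² × (8/6.5)² = 2 × 7.85 × 1.515 = 23.8, rounded up to 24, or 48 in total. The two-sided 5% level is from the SAP. Not in the documents, and assumed here: half of each arm diabetic, marker and residual SD of 1, the slopes, and a treatment shift in the marker of 0 or 0.8 SD.

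**What each term estimates.** Write M for marker change, T for treatment, D for diabetes and Y for outcome change.

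- SAP subgroup model: Y = a + b·M + c·T + d·D + e·D·T. There is one slope, b, for everyone. The coefficient e is the difference by diabetes status in the treatment effect on Y at fixed M.
- Model that answers the question: Y = a + b·M + c·T + d·D + e·D·T + f·D·M. The slope is b in non-diabetics and b + f in diabetics, and f is the difference in association.

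Suppose f is not zero but the SAP model is fitted. With half the patients diabetic, the common slope settles near b + f/2. Diabetics then keep an unmodelled slope of +f/2 and non-diabetics one of −f/2. If treatment shifts M by s in both groups, the omitted part enters the D·T coefficient as (f/2)·s − (−f/2)·s = f·s. So:

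- s = 0: the D·T term carries no information on f.
- s = 0.8, f = 1.0: expected D·T coefficient 0.80, although the marker-adjusted drug effect does not differ by diabetes. The simulated mean is 0.80.

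**Rejection rates** (simulated trials, ordinary least squares, n = 48, two-sided 5%). The last column is D·M with D·T kept in the model.

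| Truth | Marker shift | SAP term D·T | Proposed term D·M |
|---|---|---|---|
| Slope 0 vs 0.6 by diabetes | 0 | about 5% | 45–48% |
| Slope 0 vs 0.6 by diabetes | 0.8 SD | about 12% | 45–48% |
| Slope 0 vs 1.0 by diabetes | 0 | about 5% | about 87% |
| Slope 0 vs 1.0 by diabetes | 0.8 SD | about 23% | about 87% |
| Equal slopes, drug effect differs by 1 SD | 0 or 0.8 SD | about 39% | about 5% |

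The last row can be checked by hand. With 12 patients per diabetes-by-arm cell, the standard error of D·T is √(4/12) = 0.58, so a 1 SD difference gives z = 1/0.58 = 1.7, a little below 1.96, and power somewhat under one half.

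**Why D·T should stay.** If D·M is added but D·T dropped, the last-row truth with a 0.8 SD shift makes D·M reject in about 9% of trials instead of 5%. Keeping D·T removes that leak.

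**Diabetic share.** The standard error of the slope difference is roughly √(1/n_D + 1/n_ND): √(1/24 + 1/24) = 0.289 with half diabetic and √(1/12 + 1/36) = 0.333 with a quarter diabetic, about 15% larger. An uneven split lowers the power of the proposed term but does not change what either term estimates.

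**The case against.** Outcomes 4.1 does not name the interacting variable. One line covers every objective, including drug-effect objectives for which an interaction involving treatment is right. That diabetes-by-marker is meant for 3.2–3.7 is therefore an inference. It is a strong one, because those objectives are defined as associations and an interaction test on an association acts on the slope. If the sponsor wants the marker-adjusted drug effect by diabetes status, the SAP should say so, since no objective asks for it.

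The 39% in the last row is not a false-positive rate. The planned term correctly detects the drug-effect difference built into that setting. It misleads only if reported as a difference in association.

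The percentages depend on assumed slopes, SDs, diabetic share and marker shift, and the 12% and 23% need the 0.8 SD shift. That stands, so they are illustrations. The mismatch itself is algebraic.

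A reader might go further and infer that the main 3.2–3.7 models are wrong too, because objective 3.2 begins "We will assess whether the proximal renal tubular natriuretic effect of dapagliflozin leads to volume contraction compared to placebo", objectives 3.5–3.7 speak of "changes in neurohormones and volume markers with dapagliflozin compared to placebo", and the model has no treatment-by-marker term. The documents do not support that. The operational sentences ask for the association between two changes, and in 3.5–3.7 the reference to placebo can qualify the changes themselves. A regression with treatment as a covariate estimates a treatment-adjusted pooled slope: with a common slope of 0.5 the simulated mean estimate is 0.50, detected in about 89% of trials. Nowhere does the SAP say that slopes are to be compared between arms.

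**Conclusion.** The point holds for the subgroup version of models 3.2–3.7 only. The interaction named in Analysis section 4 answers a different question from the one that Outcomes 4.1 and the objectives together pose. This follows from the model terms and needs no numerical assumption. Under the stated assumptions, a slope difference of 1.0 is picked up by the planned term in about 5% to 23% of trials, depending on how far treatment shifts the marker, and by the correct term in about 87%. For a difference of 0.6 the figures are about 5% to 12% against 45–48%.

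The reach is limited: this is an exploratory subgroup analysis of exploratory associations. The main 3.2–3.7 models, the primary blood pressure model, the secondary analyses and their own diabetes interaction are untouched.

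**What to change.** In SAP Analysis section 4, for models 3.2–3.7:

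- add the product of diabetes status and marker change, where the marker change is the independent variable of that model;
- keep the diabetes main effect and diabetes-by-treatment as adjustment;
- report the slope with its 95% confidence interval in each diabetes group, and use diabetes-by-marker as the interaction test.

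Optionally, add one sentence under Analysis 3.2–3.7 stating that the target is the treatment-adjusted pooled slope. A treatment-by-marker term is needed only if the references to placebo in the objectives are meant as a comparison of slopes between arms.

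The cost is a sentence or two of SAP text and one further regression term, with no new data. Power for moderate slope differences stays low, which is acceptable for an exploratory aim if the intervals are reported and non-significance is not read as equality.
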